16.3.6 Straining

For every BM, participants will assess the degree of straining by responding to the following in the morning and evening eDiaries:

- When you pooped, how hard did you push?
 - 0 = not hard at all
 - 1 = I pushed a tiny bit hard
 - 2 = I pushed a little hard
 - 3 = I pushed hard
 - 4 = I pushed very hard

Straining will be collected twice daily (morning and evening) in the eDiary and measured using a 5-point scale. The participant's straining score in a specific analysis period will be the mean of participant's non-missing, SBM-associated straining scores during that specific period.

16.3.7 Abdominal Bloating

Abdominal bloating scores will be collected twice daily in the eDiary (morning and evening).

Abdominal Bloating - Daytime

For this parameter, participants will record their assessment of abdominal bloating during the day by responding to the following in the evening eDiary:

- From when you got up this morning until now, did your tummy FEEL big and full?
 - Yes
 - No

If “yes” then participant answers the following question:

- How big and full did your tummy FEEL?
 - 1 = a tiny bit
 - 2 = a little
 - 3 = medium
 - 4 = very

Abdominal Bloating - Nighttime

For this parameter, participants will record their assessment of nighttime abdominal bloating by responding to the following in the morning eDiary:

- From bedtime last night until now, did your tummy FEEL big and full?
 - Yes
 - No

If “yes”, then the participant answers the following question:

- How big and full did your tummy FEEL?
 - 1 = a tiny bit
 - 2 = a little
 - 3 = medium
 - 4 = very

Abdominal Bloating - Combination (Total 24-hour Period)

This parameter will be determined based on combined daytime symptoms of abdominal bloating in evening assessments and nighttime symptoms of abdominal bloating in morning assessments.

The participant's abdominal bloating score for a specific period based on evening assessments (daytime symptoms), morning assessments (nighttime symptoms), and combined morning and evening assessments will be derived as the mean of the non-missing abdominal bloating scores within the corresponding diaries during the specific period. The abdominal bloating scores of 0, 1, 2, 3, and 4 will be used to calculate the average, where '0' indicates no bloating.

16.3.8 Abdominal Pain

Abdominal pain scores will be collected twice daily in the eDiary (morning and evening).

Abdominal Pain - Daytime

For this parameter, participants will rate their abdominal pain during the daytime by responding to the following in the evening eDiary:

- From when you got up this morning until now, did your tummy hurt at all?
 - Yes
 - No

If "yes", then participant answers the following question:

- How much did your tummy hurt?
 - 1 = a tiny bit
 - 2 = a little
 - 3 = some
 - 4 = a lot

Abdominal Pain - Nighttime

For this parameter, participants will rate their abdominal pain during the nighttime by responding to the following in the morning eDiary:

- From bedtime last night until now, did your tummy hurt at all?
 - Yes
 - No

If "yes", then the participant answers the following question:

- How much did your tummy hurt?
 - 1 = a tiny bit
 - 2 = a little
 - 3 = some
 - 4 = a lot

Abdominal Pain - Combination (Total 24-hour Period)

This parameter will be determined based on combined daytime symptoms of abdominal pain in evening eDiary assessments and nighttime symptoms of abdominal pain in morning eDiary assessments.

The participant's abdominal pain score for a specific period based on evening assessments (daytime symptoms), morning assessments (nighttime symptoms), and combined morning and evening assessments will be derived as the mean of the non-missing abdominal pain scores within the corresponding diaries during the specific period. The abdominal pain scores of 0, 1, 2, 3, and 4 will be used to calculate the average, where '0' indicates no abdominal pain.

16.3.9 Fecal Incontinence - Daytime

Participants will record their episodes of fecal incontinence by responding to the following assessment in their evening eDiary.

- From when you got up this morning until now, did you have a pooping accident (even a little)?
 - Yes
 - No

16.3.10 Participant-completed Global Items

Participant-completed global change and global severity items were developed by the sponsors. The participant-completed global items consist of 4 items, 2 assessing global change in the participant's symptoms and 2 assessing the global severity of the participant's symptoms. All 4 participant-completed global items have a 7-day recall period and will be completed weekly on the eDiary device. The global severity items will be completed beginning at the Preintervention Period through End-of-Study (EOS) and the global change items will be completed beginning at Randomization through EOS.

Participant-completed Global Change Items

The 2 participant-completed global change items assess self-reported change in the participant's bowel symptoms ("pooping problems") and abdominal symptoms ("tummy problems") and are as follows:

- Compared to 7 days ago, my pooping problems today are:
 - 0 = a lot better
 - 1 = a little better
 - 2 = the same
 - 3 = a little worse
 - 4 = a lot worse

- Compared to 7 days ago, my tummy problems today are:
 - 0 = a lot better
 - 1 = a little better
 - 2 = the same
 - 3 = a little worse
 - 4 = a lot worse

Global Severity Items

The 2 participant-completed global severity items assess self-reported severity of the participant's constipation using the same child-friendly terminology as detailed for the global change items above and are as follows:

- How bad have your pooping problems been over the past 7 days:
 - 0 = I have not had pooping problems
 - 1 = a little bad
 - 2 = bad
 - 3 = very bad

- How bad have your tummy problems been over the past 7 days:
 - 0 = I have not had tummy problems
 - 1 = a little bad
 - 2 = bad
 - 3 = very bad

16.3.11 Observer-completed Global Items

The observer-completed (parents/caregivers) global items consist of 2 items, one assessing global change in the child's symptoms and the other assessing the global severity of the child's symptoms. Both observer-completed global items will be completed weekly on the eDiary device. The global severity item will be completed beginning at the Preintervention Period through the EOS and the global change item will be completed beginning at Randomization through the EOS.

Only parents/caregivers of participants 6 to 11 years of age will complete these items.

Observer-completed Global Change Item

The observer-completed global change item assesses the change in the child's constipation symptoms (1 item) as follows:

- Compared to 7 days ago, how would you rate your child's constipation symptoms today?
 - completely relieved
 - considerably relieved
 - somewhat relieved
 - unchanged
 - somewhat worse
 - considerably worse
 - as bad as I can imagine

Observer-completed Global Severity Item

The observer-completed global severity item assesses the severity of the child's constipation symptoms (1 item) as follows:

- How would you rate the severity of your child's constipation over the past 7 days?
 - none
 - mild
 - moderate
 - severe
 - very severe

16.3.12 Modified Rome III Criteria

Modified Rome III criteria will be assessed by the investigator at the Screening Visit (Visit 1) and at the end of the study intervention period at the EOT Visit (Visit 7). A participant will be considered as fulfilling modified Rome III criteria if a "yes" response is recorded to the overall question of whether the participant meets modified Rome III criteria for functional constipation. For the EOT assessment, the criteria will be assessed over the last 4 weeks of the double-blind study intervention period. In the event a participant discontinues the study prematurely, these criteria will be assessed over the last 4 weeks of double-blind study intervention, or over the duration of double-blind study intervention if less than 4 weeks.

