#### 5.1. Inclusion Criteria

The targeted participant population will include male and female participants, 6 to 17 years of age (FC participants) and 7 to 17 years of age (IBS-C participants). Randomization of FC participants will be stratified by age group only (6 to 11 years of age versus 12 to 17 years of age) with a minimum of 40% of participants within each age group. Randomization of IBS-C participants will be stratified by age group only (7 to 11 years of age versus 12 to 17 years of age) with a minimum of 40% of participants within each age group.

Participants are eligible to be included in the study only if all of the following criteria apply (unless stated otherwise, criteria apply to both FC and IBS-C participants):

1.	Age and Weight
1.01	Male and female participants must be ages 6 to 17 years (FC participants) or ages 7 to 17 years (IBS-C participants) (inclusive) at the time the participant provides assent for the study and parent/guardian/legally authorized representative (LAR) has provided signed consent
1.02	Participant weighs $\geq 18$ kg at the time the participant provides assent and the parent/guardian/LAR has provided signed consent

2.	Type of Participant and Disease Characteristics
2.01	
Participants who meet the modified Rome III criteria for Child/Adolescent FC. For at least 2 months before the Screening Visit, the participant has had 2 or fewer defecations (with each defecation occurring in the absence of any laxative, suppository, or enema use during the preceding 24 hours) in the toilet per week. In addition, participant meets one or more of the following criteria at least once per week for at least 2 months before the screening visit:
 
 
• History of retentive posturing or excessive volitional stool retention
 
• History of painful or hard BMs
 
• History of large diameter stools that may obstruct the toilet
 
• Presence of a large fecal mass in the rectum
 
• At least 1 episode of fecal incontinence per week
 

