10.1.3 Estimand Framework

Population

The target population is participants with IBS-C, ages 7-17 years old, satisfying the inclusion and exclusion criteria as specified in Sections 5.1 and 5.2 of the protocol (Version June-2020), respectively.

The analysis population is mITT as discussed in Section 6.3.

Variable

The variable is the primary efficacy endpoint defined in Section 10.1, which is 6/12 weeks APS (abdominal pain and SBM) + 2 responder as derived from twice daily responses in eDiary (morning and evening). SBM is derived based on responses for BM and rescue medication in the eDiary twice daily (morning and evening). Abdominal pain score is also derived based on responses in the eDiary twice daily for abdominal pain.

Accounting for Intercurrent Events in the Primary Efficacy Analyses

The following intercurrent events are considered for the primary efficacy analyses. All the intercurrent events are handled based on the composite strategy.

- The BMs for the participants who took a laxative, enema, or suppository on the calendar day of the BM or the calendar day before the BM will not be considered as SBMs for the analysis.
- Participants who discontinue prematurely during but prior to the completion of the double-blind Study Intervention Period will have their eDiary data included up to the morning diary following the last dose date for primary endpoint. The early discontinued participants will be considered non-responders for the following weeks for primary endpoint.
- eDiary responses following the onset of dose de-escalation will not be included. The participants with dose de-escalation will be considered non-responders for the subsequent study intervention weeks (after the onset of dose de-escalation) for the primary endpoint based on the randomized study intervention group.
- A participant has to have at least 4 completed diary days per study intervention week to be considered a responder for that week and otherwise, the participant will be considered non-responder for that week. A completed diary day is a day in which both morning and evening eDiary entries are filled out by a study participant.

Population-level Summary

The population-level summary for the primary endpoint is the proportion of participants satisfying the APS + 2 responder criteria for at least 6 out of 12 weeks during the study intervention period for each linaclotide dose.

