Serum Pregnancy Tests ⁿ	X							
Urine Pregnancy Tests ^o			X		X	X	X	
Urine Drug Screen ^p	X							
AE Evaluation	X	X	X	X	X	X	X	X
Prior and Concomitant Medications	X	X	X	X	X	X	X	X
Rescue Medication Dispensed ^q		X	X	X	X	X	X	
eDiary and Instructions Given to Participant/Caregiver ^r		X						
eDiary Compliance ^r			X	X	X	X	X	X
eDiary Eligibility Report ^f			X					
Study Intervention Administered on Site ^s			X					
Study Intervention Dispensed			X		X	X		
Study Intervention and Rescue Medication Compliance and Accountability			X ^s	X	X	X	X	X ^t

AE = adverse event; ECG = electrocardiogram; eDiary = electronic diary: refers to the participant- or interviewer-administered version of the PRO diary on a handheld electronic device; IWRS = interactive Web response system; PRO = patient reported outcome.

- a. Study procedures for screening in LIN-MD-66 can be combined with End of Treatment (EOT)/Week 12 Visit (Visit 7) for Study LIN-MD-64.
- b. Participants who rollover to the long-term safety study, LIN-MD-66, before the EOS Visit (Visit 8) are not required to have this visit.
- c. Participants must complete at least 12 weeks (84 days) of study intervention before arriving at the study site for the EOT/Week 12 Visit (Visit 7). All randomized participants who prematurely discontinue from the study intervention, regardless of cause, should complete assessments at this EOT/Week 12 Visit (Visit 7).
- d. The parent/guardian/legally authorized representative must provide written informed consent and the participant must provide assent before the participant's enrollment in the study. If a parent or legal guardian is also the participant's caregiver, he or she will be asked to sign a combined parent and caregiver written informed consent. Caregivers other than parent or legal guardian must provide written informed consent.
- e. Prior to dosing, the investigator or appropriate site staff member will assess if Rome IV criteria for Child/Adolescent FC (FC and IBS-C participants) or Rome IV criteria for Child/Adolescent IBS (IBS-C participants) was met and record the outcome in the eCRF. Eligibility for the study is not based on this assessment.
- f. Eligibility report must be run prior to randomization.

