Overall SBM responders are defined as participants who have a change from baseline of ≥ 2 SBMs/week in the 12-week SBM frequency rate over the Intervention Period.

The above response threshold of at least 2-point change from baseline in 12-week SBM frequency rate (SBMs/week) to define the overall SBM responder may be revisited before unblinding based on the findings of blinded psychometric analysis to determine within participant clinically meaningful change. If this is the case, the revised response threshold will be documented in a SAP amendment.

To be qualified for an overall SBM responder, a participant must also meet the following conditions simultaneously:

- At least 4 weeks of study intervention duration,
- At least 48 completed diary days during the 12-week Study Intervention Period, and
- At least 4 completed diary days per analysis week in the last 4 intervention weeks

The participant needs to fill out both morning and evening diary on the same day to have a completed diary day.

The proportion of responders in the linaclotide group will be compared with the proportion in the placebo group using a CMH test controlling for age group (6 - 11 years of age versus 12 - 17 years of age). Participants who are not assessable for the responder parameters due to missing information are considered non-responders. The number and percentage of responders for each study intervention group, the difference in responder rates between the linaclotide group and the placebo group, the corresponding 95% confidence interval, Mantel-Haenszel based odds ratio and corresponding 95% confidence interval, and the 2-sided p-value associated with the CMH tests will be presented.

Weekly SBM + 2 Responder During the Study Intervention Period

For any week in the study intervention period, a weekly SBM + 2 responder is a participant who has an SBM increase ≥ 2 in the SBM weekly rate from baseline for that week. For the analysis week, if a participant did not have at least 4 full days (with both completed morning and evening diaries) of diary entries, the participant will not be considered a weekly SBM + 2 responder for that corresponding week.

The threshold of at least 2 to define the weekly SBM responder may be revisited before unblinding based on the findings of blinded psychometric analysis to determine within participant clinically meaningful change. If this is the case, the revised response threshold will be documented in a SAP amendment.

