The observer-completed global change item and global severity item will be assessed on a weekly basis in the eDiary, for the 6 - 11 years of age group only as discussed in Section 16.3.11. Summary statistics of observer-completed global items will be provided by study intervention group in the 6 - 11 years of age group at each week during the Study Intervention Period. Counts and percentages for each category of global change item and global severity item will be provided by study intervention group.

Proportion of Participants Who No Longer Fulfill Modified Rome III Criteria for FC at the End of the Study Intervention Period

The details of the derivation of this endpoint are discussed in Section 16.3.12. The proportion of participants who no longer fulfill modified Rome III criteria for FC at the end of the study intervention period will be presented by study intervention group.

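### The end-of-treatment Rome III endpoint sets no minimum treated time, so a child who stops within days can be counted as no longer meeting the diagnosis

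*SAP*

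**What the plan says.** FC SAP 16.3.12 has the investigator assess the modified Rome III criteria at Screening and at Visit 7. The Visit 7 assessment looks back over the last 4 weeks of double-blind treatment. For a child who discontinues, it covers the last 4 treated weeks, "or over the duration of double-blind study intervention if less than 4 weeks". IBS-C SAP 16.3.9 and Protocol 8.1.1.3 and 8.1.2.3 carry the same rule. Status rests on one answer: a child fulfills the criteria if a yes "response is recorded to the overall question of whether the participant meets modified Rome III criteria for functional constipation".

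Early discontinuers are meant to have this assessment. Under FC SAP 4.0 (Table 4-1, footnote c), "All randomized participants who prematurely discontinue from the study intervention, regardless of cause, should complete assessments" at Visit 7.

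For the analysis, FC SAP 10.3 says only this, with one figure for each arm: "The proportion of participants who no longer fulfill modified Rome III criteria for FC at the end of the study intervention period will be presented". IBS-C SAP 10.3 is equivalent. For this endpoint neither SAP gives a minimum exposure, a rule for discontinuers or a rule for a missing Visit 7 answer. Only the general observed-cases statement applies.

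At entry the time base is much longer. Protocol 5.1, criterion 2.01 reads: "For at least 2 months before the Screening Visit, the participant has had 2 or fewer defecations" in the toilet per week. At least one supporting feature must also have been present "at least once per week for at least 2 months before the screening visit". IBS-C participants must in addition meet the IBS criteria over the same 2 months (criterion 2.011).

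**The concern.** The criteria are weekly frequencies, and the documents do not say how to apply them to a window of a few days. A child with several loose stools in that window is unlikely to look as if stools are infrequent. The supporting features may also be absent simply because there was little time for them to occur. A child who leaves because of the drug's most frequent adverse event can then be counted among those free of the diagnosis.

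The plan guards its other responder endpoints against this. FC overall SBM response requires, among other conditions, "At least 4 weeks of study intervention duration" (FC SAP 10.3), and participants who cannot be assessed are non-responders. For the IBS-C primary endpoint, "The early discontinued participants will be considered non-responders for the following weeks for primary endpoint" (IBS-C SAP 10.1.3). What is at stake is the meaning of a proportion that readers will probably take as remission.

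**Working it through.** No sample size, power or alpha figure depends on this rule, so there is no planned figure to reproduce. The check has four parts.

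**1. The same child under three rules.** Take a child treated for less than 4 weeks.
- FC overall SBM responder: non-responder, because the 4-week exposure condition fails.
- IBS-C primary endpoint (6 of 12 weeks): at most 4 weeks can be responder weeks, and 4 < 6, so non-responder.
- Rome III endpoint: assessed over the treated days, and counted as no longer fulfilling if the answer is no.

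**2. What a short window does to weekly criteria.** This is illustrative and assumes Poisson counts with an unchanged underlying rate.
- If the count is scaled to a week, one defecation in 3 days is 1 × 7/3 = 2.33 per week, already above the limit of 2.
- At an assumed true rate of 1.5 per week, the chance of exceeding the limit over 3 days is 1 − exp(−1.5 × 3/7) = 47%. Over 28 days (mean 6, more than 8 needed) it is 15%. Windows of 4 and 5 days give 21% and 29%.
- Across assumed rates of 0.5 to 2 per week, the 3-day figure runs from 19% to 58%.
- If instead the raw count must exceed 2, the 3-day figure is only 0.1% to 5.6%. A child with 3 or more stools exceeds the limit on either reading.
- A supporting feature averaging once a week is absent with probability exp(−3/7) = 65% over 3 days and exp(−4) = 1.8% over 28 days.

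**3. Effect per child.** With the planned arm sizes (163 per FC arm; 50 per IBS-C arm):
- FC: 1/163 = 0.61 percentage points.
- IBS-C: 1/50 = 2.0 percentage points.

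**4. How many children.** Protocol 2.2.2 reports one linaclotide discontinuation for diarrhea in each 4-week Phase 2 study.
- LIN-MD-62: 1 of 116 + 16 = 132.
- LIN-MD-63: 1 of 74 + 8 = 82.
- Pooled: 2/214 = 0.93%, exact (Clopper-Pearson) 95% CI 0.11% to 3.3%.
- FC linaclotide arm: 163 × 0.0093 = 1.5 children (0.2 to 5.4).
- IBS-C arm: 50 × 0.0093 = 0.5 children (0.1 to 1.7).

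If every such child is recorded as no, would otherwise have fulfilled the criteria, and has no counterpart on placebo, the shift equals the discontinuation rate: about 0.9 points, and 3.3 points at the upper limit.

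**The case against.** The strongest reply is that the rule is a deliberate while-on-treatment choice. The FC primary endpoint does the same: FC SAP 10.1.4.1 treats a discontinuer's rate over the treated days as equivalent to the 12-week rate. The Rome III result is one of the other efficacy endpoints, outside the sequential procedure, with no named test. This stands as a limit on importance. It does not explain how criteria defined by the week are to be judged over 3 days, or why overall SBM response needs 4 weeks and this endpoint does not.

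Four stronger readings are tempting, and the documents do not support them.
- *That stopping for diarrhea is always scored as remission.* The result is an investigator's overall judgment, and the text does not dictate a no. The child can be counted this way, not must be.
- *That the inflation is several points.* A reader might carry over the diarrhea incidence: 7.6% versus 0% in LIN-MD-62, or 19.2% versus 7.0% at 72 µg in the adult study MCP-103-309. Incidence is not discontinuation, and in Phase 2 most pediatric diarrhea was mild. The short window also applies to dropouts for any reason, including on placebo; one placebo child in LIN-MD-63 stopped for adverse events.
- *That the higher IBS-C dose is favored.* The adult study LIN-MD-01 found diarrhea incidence not dose related, both IBS-C arms allow blinded dose reduction, and the doses are not tested against each other.
- *That every early discontinuer should count as a failure.* A child who stops in week 11 has a full 4-week assessment, and overriding it would create the opposite misclassification.

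**Conclusion.** The concern holds in limited form. The assessment window has no lower bound, nothing elsewhere in either SAP supplies one for this endpoint, and a child treated for a few days can be counted as no longer meeting the diagnosis.

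On Phase 2 discontinuations the effect is about 1 percentage point and at most about 3. That assumes the Phase 2 rate carries over, although those studies used different doses and lasted 4 weeks. It also assumes that each affected child is misclassified and that no placebo child is. In FC the likely direction favors linaclotide, because diarrhea was more frequent on drug. In IBS-C no direction between doses can be claimed.

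The primary and secondary conclusions, alpha and power are untouched. This is an inexpensive improvement to a descriptive endpoint.

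A neighboring gap has the same remedy. Because only a yes counts as fulfilling, a missing Visit 7 answer could be dropped as not observed or read as no longer fulfilling, and the SAPs do not say which.

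**What to change.** In FC SAP 10.3 and 16.3.12, and IBS-C SAP 10.3 and 16.3.9, state the following.
- mITT participants with less than 4 weeks of double-blind intervention, or with no Visit 7 Rome III answer, count as still fulfilling the criteria.
- All mITT participants are in the denominator.
- For those who stop after at least 4 weeks, the Visit 7 answer stands as recorded.
- The fully as-assessed proportion is shown as a supportive line.

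The 4-week threshold is the plan's own, from the FC overall SBM responder rule. The cost is a few sentences in each SAP and one extra table line; visits and data collection do not change. The downside is that reported proportions become slightly less favorable in all arms, and a child who truly improved but stopped before 4 weeks, or a completer with a missing answer, is scored conservatively. The supportive line shows how much this matters.
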